3 INVESTIGATIONAL PLAN

3.1 Overall Trial Design

3.1.1 Trial Design Diagram

A trial design diagram is provided in [Figure 1](#).

^a Gestational age 24 weeks + 0 days to 34 weeks + 2 days.

^b Informed consent form (ICF) should be signed as soon as possible after delivery. Initial eligibility check must be completed within 144 hours of delivery.

^c Randomization occurs between 96 and 192 (+4) hours of delivery. Treatment is administered intra-nasally as 1 spray in each nostril approximately 5 to 10 minutes before each milk expression session.

^d In this trial, treatment days start from the time of randomization, with Day 1 being the first 24 hours after randomization, Day 2 being 24 to 48 hours after randomization, and so on. The treatment period includes 14 such consecutive intervals of 24 hours from the time of randomization, corresponding to 14 treatment days (Days 1 to 14). Maternal subjects should stop the administration of IMP as soon as having completed 14 days' treatment, rather than continue dosing until the Day 15/End-of-Treatment visit. Day 3, Day 10, Day 15/End-of-Treatment and Day 18/Follow-up visits can be postponed a maximum of 2 days.

^e Maternal subjects will attempt to express milk at least 5 times every 24 hours during the observation period and 6 to 8 times every 24 hours during treatment and follow-up periods, including at least once during the night and with no more than 5 hours between milk expression sessions.

^f MoM volume from the first milk expression session up to Day 18/Follow-up visit will be recorded.

^g Infant's discharge from NICU or until the last milk expressed during maternal subject's treatment with IMP is either consumed or discarded, whichever occurs last. Long-term follow-up of infants through 24 months of corrected gestational age (section 3.6.8).

Abbreviations: ICF=informed consent form, min.=minimum, IMP=investigational medicinal product, MoM=mother's own milk, NICU=neonatal intensive care unit.

Figure 1 Overall Trial Design

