3.1.2 Overall Design and Control Methods

This is a randomized, double-blind, placebo-controlled, multicenter trial exploring the efficacy and safety of intra-nasal administration of 400 µg merotocin in increasing milk production in women with preterm delivery and inadequate initial milk production.

The trial population consists of maternal subjects who have delivered a preterm singleton (gestational age from 24 weeks + 0 days to 34 weeks + 2 days), who wish to provide MoM to their infants but have inadequate initial milk production and who are willing to express milk 6 to 8 times every 24 hours throughout the trial. No specific trial procedures are required for infants.

[figure not shown]
The trial consists of a screening period, a treatment period and a post-treatment follow-up period. In addition, there is a post-trial follow-up of infants.

- Screening Period: The screening period starts from the signing of informed consent and ends at randomization, which occurs between 96 to 192 (+4) hours of delivery. The screening period must include an observation period of a minimum of 48 hours for the collection of milk expression data.
- Treatment Period: Once the observation period is completed, eligible women will be randomized in a 1:1 ratio to receive either merotocin or placebo. The treatment period is 14 days and includes visits on Days 3 and 10, as well as an End-of-Treatment visit on Day 15 or the day after the last dose of investigational medicinal product (IMP) in case of premature discontinuation.
- Post-treatment Follow-up Period: The post-treatment follow-up period includes a Day 18 / Follow-up visit, scheduled 3 days after the Day 15/End-of-Treatment visit.

Note that Day 3, Day 10, Day 15/End-of-Treatment and Day 18/Follow-up visits can all be postponed for a maximum of 2 days.

Trial Activities

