4 SELECTION OF TRIAL POPULATION

4.1 Trial Population

4.1.1 Inclusion Criteria

Inclusion criteria for entry into observation period:

Maternal subject:

1. Signed and dated informed consent for the maternal subject and parental consent for the infant prior to any trial activity.
2. Aged 18 to 44 years at the time of informed consent.
3. Delivered at the hospital system associated with the trial center.
4. Delivered a preterm singleton at a gestational age of 24 weeks + 0 days to 34 weeks + 2 days.
5. Attempted initial milk expression within 12 hours of delivery.
6. Attempted milk expression at least 3 times every 24 hours from 24 hours of delivery to the start of observation period (at least 3 times between 24 and 48 hours of delivery for subjects who enter the observation period within 48 hours of delivery).
7. Is willing to express milk at least 5 times every 24 hours during the observation period and 6 to 8 times every 24 hours during the treatment and post-treatment follow-up periods, including at least once during the night and with no more than 5 hours between milk expression sessions, during the trial (up to 23 days).
8. Is willing to refrain from sexual intercourse during the trial.

Inclusion criteria for randomization (in addition to the criteria above):

Maternal subject:

9. Attempted milk expression using the breast pump at least 5 times every 24 hours for the last 48 hours of the observation period, i.e., the 48 hours prior to the last pumping session before randomization.
10. Accurately recorded timing of milk expression after providing informed consent.
11. Produced <200 mL milk for the last 24 hours of the observation period (the 24-hour baseline interval), i.e., the 24 hours prior to the last pumping session before randomization.
12. Delivered 96 to 192 (+4) hours prior to randomization.

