6.3 Randomization

Randomization of eligible maternal subjects will occur at 96 to 192 (+4) hours of delivery. Every effort should be made to randomize maternal subjects as early as possible, but not earlier than 96 hours of delivery.

Maternal subject-related activities at the randomization visit:

End of observation period

- Provide detailed and standardized lactation instructions, support, and training in how to weigh milk.
- Have maternal subject express milk at the site and record the milk expression properly on the milk container label, in accordance with instructions provided in the lactation manual
- Weigh the milk collected during the observation period, including the milk from the milk expression session just performed, in accordance with instructions provided in the milk weighing procedures manual
- Review milk expression documentation for completeness and compliance
- Perform remainder of inclusion and exclusion criteria check (prohibited therapy listed in Section 4.3.2)
- Perform physical examination
- Measure vital signs (sitting blood pressure and heart rate)
- If the maternal subject is still eligible and if the amount of available milk exceeds the needs of the infant, collect a milk sample for analysis of milk composition (Section 7.3.2). Sample should be taken from the milk expressed at the trial center prior to randomization

Randomization

- Randomly assign the trial treatment to the maternal subject through the e-CRF
- Prime and weigh each nasal spray bottle before dispensing the IMP kit
- Have maternal subject administer first dose of trial medication at the trial center, express milk, and record the milk expression properly on milk container labels in accordance with instructions provided in the lactation manual for subjects
- Instruct maternal subject to bring all the milk collected (if it has not been brought to the trial center), her nasal spray bottles, and the milk container labels with recordings of the milk expression to the trial center at the Day 3 visit
- Record concomitant medications
- Collect and record AEs

Infant-related activities at the randomization visit:

Prior to randomization

- Ensure infant exclusion criteria check is performed

Randomization

Collect the following data from hospital records:

- Record infant body weight (for the day of randomization or last recorded value as available)

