9.1 Determination of Sample Size

The primary objective of this trial is to evaluate the effect of merotocin on increasing milk production in women with preterm delivery. The comparison is based on the primary endpoint of the volume of MoM produced over Days 1 to 14.

Since neither the onset nor the duration of effect of merotocin is known, the initial sample size calculation is based on a comparison of the time-averaged difference between the merotocin group and the placebo group over Days 1 to 14. A sample size of 100 maternal subjects, allocated equally to each treatment group, will provide roughly 80% power to detect a 50% increase in the volume of MoM produced over Days 1 to 14, compared to placebo.

The primary analysis of the volume of MoM obtained over Days 1 to 14 will be based on a repeated measures ANCOVA. For a given sample size, the power is a function of the assumed (constant) treatment effect and the assumed correlation of observations within subjects. The power for a sample size of 100 maternal subjects equally distributed between the two treatment groups for various combinations of correlation and treatment effect is shown in [Table 7](#). As shown in the table, a sample size of 100 subjects has approximately 80% power to detect a 50% increase in the volume of MoM produced, unless the within subject correlation is greater than 0.8.

Table 7 Power for Various Combinations of Correlation and Treatment Effect

Correlation	Treatment effect ^a (merotocin relative to placebo)		
	30% increase	40% increase	50% increase
0.6	64.2 %	81.1 %	92.3 %
0.7	57.2 %	74.4 %	86.1 %
0.8	52.1 %	66.5 %	80.2 %

^a Assuming 100 subjects will be equally distributed between the two groups, with a uniform 30% drop-out rate in the trial.

The results presented in [Table 7](#) are based on simulations. For each scenario, 1,000 datasets with 100 subjects equally distributed between the 2 treatment groups were generated. In each simulation, 14 observations from a multivariate log-normal distribution were generated for each subject. The means and variances of the multivariate log-normal distribution used to draw samples from, were based on external data received by Ferring. The correlation between the volume of MoM expressed

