9.6 Endpoint Assessments

9.6.1 General Considerations

Statistical analysis will be performed using SAS software Version 9.2 or later (SAS Institute, Inc, Cary, North Carolina) unless stated otherwise.

Analysis and Presentation of Primary and Secondary Endpoints

Results for the primary endpoint and secondary efficacy endpoints will be presented for both the FAS and the PP analysis sets. The primary endpoint and selected secondary efficacy endpoints will also be presented by gestational age group (<27 weeks and \geq 27 weeks).

Continuous variables will be summarized using the mean, standard deviation, median, minimum value and maximum value. Categorical variables will be summarized using frequency counts and percentages. All primary and secondary efficacy endpoints will be presented in data listings.

Treatment differences will (where appropriate) be presented with 95% two-sided confidence intervals and p-values corresponding to the statistical test of the hypothesis ‘equal effect’ against the alternative ‘different effect’. All statistical tests will be performed using a two-sided test at a 5% significance level, unless otherwise stated.

Multiplicity

Concerning the secondary efficacy endpoints, no formal adjustment for multiplicity will be utilized. Statistical significant results will be interpreted cautiously.

Missing Data

Missing data on the primary endpoint will not be imputed for the primary analysis. As this is a PoC trial, the interest is in assessing the difference in the amount of MoM expressed during treatment adherence. Furthermore, the repeated measures ANCOVA model is robust against dropouts under the assumption that the drop-out is not related to treatment. The reason for premature discontinuation will be compared between treatment groups. Sensitivity analyses examining the robustness of the primary analysis results with respect to the above missing data assumption will be carried out by imputing missing data under a missing-not-at-random (MNAR) assumption. The imputation will be carried out using the pattern mixture model with control based pattern imputation.³²

Missing values for the secondary endpoints will not be imputed.

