9.6.2 Primary Endpoint

Primary Endpoint: Primary Analysis

The primary objective of this PoC trial is to evaluate the effect of merotocin on increasing milk production in women with preterm delivery. The primary endpoint of the trial is the volume of MoM produced over Days 1 to 14.

Repeated Measures ANCOVA Model:

The primary endpoint will be analyzed using a repeated measures ANCOVA with a general (unstructured) covariance matrix. The daily volume of MoM produced will be the dependent

variable. The model will include the baseline volume of MoM produced as covariate, with treatment group, treatment day, treatment-by-day interaction, and gestational age group (<27 weeks and \geq 27 weeks) as factors. The baseline volume of MoM produced is defined as the volume obtained at the 24-hour interval for eligibility during the observation period. The average treatment effect across treatment days and the within-day treatment effect will be reported along with the corresponding two-sided 95% confidence intervals and p-values.

The analyses based on the FAS will be considered the primary, while the analyses based on the PP analysis set will be considered supportive. PoC will be considered to be established if the repeated measures ANCOVA model results in a significant positive average treatment effect of merotocin compared to placebo across the treatment period in the FAS.

Primary Endpoint: Sensitivity/Supportive Analyses

The Safety Committee may choose to reduce the dose in case of any safety concerns. In that case, the analyses will be performed both by combining the merotocin dose groups into one and by using the actual merotocin dose groups separately.

Sensitivity analyses exploring the impact of the missing data assumption on the results of the primary analysis will be performed for the FAS and PP analysis sets. Missing data will be imputed under a MNAR assumption using the pattern-mixture model with control-based pattern imputation.

The sensitivity of the results with respect to choice of the covariance structure will be investigated using more restrictive covariance structures (compound symmetry, Toeplitz, separate compound symmetry for each treatment group, and separate Toeplitz pattern for each treatment group). Nested models will be compared using the likelihood ratio test. In addition, interactions of treatment and gestational age group will be tested in the model with a general covariance structure.

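### The primary model adjusts only for the last 24 hours of baseline milk; the preceding 24-hour volume can be derived by design and might sharpen the estimate at small cost

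*Combined protocol and SAP*

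**What the plan says.** The primary analysis is a repeated measures ANCOVA on daily volume with an unstructured covariance matrix. Its terms are baseline volume, treatment, day, treatment-by-day and gestational age group. Section 9.6.2 fixes the covariate: "The baseline volume of MoM produced is defined as the volume obtained at the 24-hour interval for eligibility during the observation period". Inclusion criterion 11 requires that same volume to be below 200 mL.

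Several provisions make the preceding day available as well:

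- Section 3.1.2 sets an observation period of at least 48 hours.
- Criterion 9 (Section 4.1.1) reads "Attempted milk expression using the breast pump at least 5 times every 24 hours for the last 48 hours of the observation period", and criterion 10 requires accurately recorded session times.
- Table 5 (Section 7.1.1) has pumped milk bottled separately by session.
- Section 6.3 tells staff to "Weigh the milk collected during the observation period, including the milk from the milk expression session just performed".
- A note to Figure 1 (Section 3.1.1) adds that "MoM volume from the first milk expression session up to Day 18/Follow-up visit will be recorded".

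The earlier volume appears neither in the primary model nor among the eight additional covariates that Section 9.6.2 lists for supportive adjustment. No reason is given for leaving it out.

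**The concern.** Proof of concept rests on one test of the average treatment effect, in a trial where "A sample size of 100 maternal subjects, allocated equally to each treatment group, will provide roughly 80% power to detect a 50% increase". Section 9.9 puts overall power at 77.2% once the futility look is included, at a correlation of 0.8. Precision therefore matters.

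The single milk covariate covers one day and has a restricted range, because women are selected on it. Randomization spans 96 to 192 (+4) hours after delivery, so the same volume can belong to a woman whose supply is still rising or to one whose supply has levelled off. A second pre-randomization day carries some information on level and rate of rise. If it predicts the 14-day mean beyond what the last day already explains, leaving it out keeps avoidable between-woman variance in the residual.

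**Working it through.** **Inputs from the protocol.** Two-sided 5% level (Section 9.6.1); 100 women, 1:1; constant within-subject correlation r of 0.6, 0.7 or 0.8 over 14 simulated treatment days; 30% drop-out (Section 9.1). Not given: the log-normal means and variances, and any correlation between baseline and treatment days.

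**Step 1: the plan's own figure.** The 80.2% in Table 7 (r = 0.8, 50% increase) cannot be rebuilt without those means and variances. I solved for a single SD from that cell and predicted the other eight. Only one came within 2 points (r = 0.7, 50% increase: 84.5-84.7% against 86.1%). That approximation is inadequate, and the mismatch is not evidence against the table.

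**Step 2: does Table 7 reflect baseline adjustment?** Convert power to z = Φ⁻¹(power) + 1.96. In the 50% column, 92.3% gives 3.386 and 80.2% gives 2.809, a ratio of 0.83. The other two columns give 0.84 and 0.87. Under constant correlation, ignoring drop-out, the expected ratios are:

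- no baseline term: √(0.6286/0.8143) = 0.88, so 92.3% at r = 0.6 would become about 84.5% at r = 0.8;
- one baseline with the same correlation: √(0.2686/0.1743) = 1.24, so 92.3% would become about 98.8%.

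Table 7 falls to 80.2%. It looks like a calculation with no baseline term, and Section 9.1 describes no baseline draw. It therefore gives no support for constant correlation back to baseline.

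**Step 3: gain if constant correlation did reach baseline (an assumption).** Variance of the 14-day mean, in units of the daily variance:

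- given one baseline: (1 + 13r)/14 − r²
- given two: (1 + 13r)/14 − 2r²/(1 + r)

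| r | one | two | variance cut | SE ratio |
|---|---|---|---|---|
| 0.6 | 0.6286 − 0.3600 = 0.2686 | 0.6286 − 0.4500 = 0.1786 | 34% | 0.815 |
| 0.7 | 0.7214 − 0.4900 = 0.2314 | 0.7214 − 0.5765 = 0.1450 | 37% | 0.791 |
| 0.8 | 0.8143 − 0.6400 = 0.1743 | 0.8143 − 0.7111 = 0.1032 | 41% | 0.769 |

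With log-normal volumes cut at 200 mL (assumed log-SD 0.6-0.9, assumed median 120 mL), the SE ratio is 0.78-0.85. Together these make the interval about 15-23% narrower.

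**Step 4: gain under other structures (all assumed).**

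- AR(1): SE ratio 1.000, because the last day screens off the day before it. It stays 1.00 with the 200 mL cut.
- Random intercept plus AR(1), intercept share 0.3-0.7, AR parameter 0.5-0.9: SE ratio 0.925-0.999, so at most 1 − 0.925² = 14% of variance. In the two combinations also run with the cut (0.5 with 0.8; 0.3 with 0.9) it is 0.99-1.00.
- Simulated ramp-up of supply: 0% to about 20% of residual variance. At 20% the SE ratio is √0.80 = 0.89. This is the range in the models tried, not a bound.

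**Step 5: the downside.** With about 96 residual degrees of freedom (100 women less intercept, treatment, gestational age group and baseline), a useless covariate multiplies the SE by √(96/95) = 1.005. Break-even is a partial correlation of √(1 − 95/96) = 0.10. If missing earlier volumes removed 3 of 100 women, the SE would rise by √(100/97) = 1.015, which is why a missing-value rule is needed.

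**The case against.** The strongest reply is that the planned model is valid, prespecified and coherent, and that the settings closest to early lactation give little. Supply is still being established, and Section 3.6.1 itself raises delayed onset of lactogenesis II, so decaying correlation is plausible. The earlier day is also not a like-for-like second baseline. For the earliest women it falls at roughly 48-72 hours after delivery; for the latest, at 144-168 hours or later. With the minimum observation period it is also the day the regimen changes, from at least 3 attempts per 24 hours to at least 5 by pump. All of this stands. It lowers the expected gain but introduces no bias, since the value precedes randomization.

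A reader might infer more than the documents support:

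- *That every randomized woman has 48 hours of weighed milk.* Criterion 9 requires attempts, not volumes. Milk fed before weighing is noted as a fed volume, breastfed milk comes from infant weighing (Section 3.1.2), and Section 4.2.2 describes automatic calculation only for the last 24 hours.
- *That the change is free.* It needs no new data collection, but it does need a derivation, a missing-value rule and one degree of freedom.
- *That a cut of about 40% in variance follows from the plan's own assumption.* The plan assumes constant correlation for Days 1 to 14 only, and Step 2 tells against extending it. The statement that power holds "unless the within subject correlation is greater than 0.8" likewise concerns treatment days.
- *That power would rise by a stated amount.* Table 7 appears to take no credit for any baseline, so it offers no sound starting point for that conversion.
- *That the trial is underpowered or its test flawed.* Drop-out is already in the stated power, and the range restriction weakens the covariate without invalidating it.

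**Conclusion.** The point holds as a low-severity efficiency improvement. Type I error, bias and interpretation of the planned test are unaffected. The potential gain runs from nothing (AR(1)), through 0% to about 20% of residual variance (ramp-up models), to about 40% with an interval about 15-23% narrower, the last only under constant correlation back to baseline. The documents do not say which case applies. The case for the change is asymmetry: about 0.5% on the SE if the covariate proves uninformative, against a possible material gain, provided no woman is lost through a missing value.

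**What to change.** In Section 9.6.2 and the synopsis, define the volume from 48 to 24 hours before the last pumping session and prespecify it as a second baseline covariate in the primary model. State that noted fed volumes, infant-weighing amounts and hand-expressed milk are counted as they are for the last 24 hours. Add a treatment-blind rule for missing values, for example imputation from the pooled baseline data of both arms, so that no woman leaves the model. Fix all of this before any unblinded interim look. If that is no longer possible, or the primary model is to stay as it is, name the two-baseline model as a sensitivity analysis instead.

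Cost: protocol and SAP wording, one derived variable from data already collected, the missing-value rule and one degree of freedom.

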3.6 Discussion of Overall Trial Design and Choice of Control Groups

3.6.1 Trial Design

This trial will investigate the efficacy and safety of repeated intra-nasal administrations of merotocin compared to placebo in increasing milk production in women with preterm delivery and inadequate initial milk production.

The trial design employs best practices for establishing an adequate milk supply. All maternal subjects will institute a high frequency milk expression regimen and will receive standardized lactation counselling and ongoing support consistent with guidelines for promoting lactation in this population.

There is no approved product for women with lactation deficiency in the country where the trial will be conducted. Some pharmacologic agents are used in clinical practice to increase milk supply, but there is only limited medical evidence to support the safety and efficacy of the use of these agents to correct lactation deficiency in women with preterm delivery.^{25,26,27} For these reasons, a placebo comparator is necessary to evaluate the potential of merotocin to increase milk production in this population.

The window for randomization, originally set to 96 to 144 hours of delivery, was chosen to enhance the probability of selecting maternal subjects who truly have an inadequate milk supply but also to ensure that intervention is instituted early enough in the postpartum period to have an impact. By the amendment (dated 06-04-2022), the window was expanded to 96 to 192 (+4) hours of delivery to allow adequate time for the maternal subjects to appreciate and understand the value of participating in the trial, with a negligible risk for any negative impact on induction of lactation. Allowing randomization earlier in the postpartum period might select maternal subjects, whose milk supply appears inadequate due to delayed onset of lactogenesis II but who may ultimately establish an adequate milk supply without intervention.

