Although the randomization will be stratified by site, it will not be included in the model for the primary analysis because issues may arise when adjusting for a large number of small centers (with respect to the number of randomized subjects). Additionally, common methods, such as pooling small centers together to form one large center, lack scientific justification. To ensure that the trial conclusions are not substantially affected by this exclusion, sensitivity analyses will examine the relationship between the effect of treatment and center. This will be carried out by including center and the center*treatment interaction as factors in the repeated measures ANCOVA model specified for the primary endpoint.

Sensitivity analyses will be performed to assess the relationship between the time of randomization from delivery and the effect of treatment on the volume of MoM produced over Days 1 to 14. This will be carried out by including the time of randomization from delivery and the time of randomization from delivery by treatment interaction in the repeated measures ANCOVA model specified for the primary endpoint.

The above primary analysis will be repeated to examine the consistency of the relationship between treatment and the volume of MoM produced over Days 1 to 14 after having adjusted for additional covariates (age of maternal subject, ethnicity, presence of fetal growth restriction, birth weight, caesarean section, primipara versus multipara, use of antenatal steroids and pre-pregnancy BMI). Each covariate will be added to the model one by one and tested at a two-sided significance level of 20%. In case two or more covariates are significant at the 20% level, a forward selection process will be applied with a threshold for adding effects at a two-sided significance level of 20% to identify the final model.

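### Adding hours from delivery to randomisation to the primary model would be a cheap, modest precision gain now that the randomisation window has doubled

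*Combined protocol and SAP*

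**What the plan says.** Section 3.6.1 gives the history of the window: "The window for randomization, originally set to 96 to 144 hours of delivery"; by the amendment dated 06-04-2022, "the window was expanded to 96 to 192 (+4) hours of delivery". Section 7.1.1 counts treatment days in 24-hour blocks from randomisation, not from delivery.

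Section 9.6.2 (and the synopsis in the same terms) defines the primary analysis: "The model will include the baseline volume of MoM produced as covariate, with treatment group, treatment day, treatment-by-day interaction, and gestational age group". Time from delivery is not among these terms. Section 4.2.2 stratifies by gestational age group and site only. The further covariates to be screened in section 9.6.2 are "age of maternal subject, ethnicity, presence of fetal growth restriction, birth weight, caesarean section, primipara versus multipara, use of antenatal steroids and pre-pregnancy BMI", and timing is not one of them.

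Timing appears once in the planned analyses, as a sensitivity analysis "to assess the relationship between the time of randomization from delivery and the effect of treatment on the volume of MoM produced". It is carried out by "including the time of randomization from delivery and the time of randomization from delivery by treatment interaction" in the primary model.

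**The concern.** Two women with the same 24-hour baseline volume can enter Day 1 about four days apart in postpartum age. The treatment-day factor cannot absorb that difference, because it starts from randomisation for everyone. Baseline volume may absorb part of it, but eligibility holds baseline below 200 mL whatever the time since delivery, so its range is limited.

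The plan's own reasoning makes a link with later volume plausible. Section 3.6.1 warns that randomising earlier might select women "whose milk supply appears inadequate due to delayed onset of lactogenesis II but who may ultimately establish an adequate milk supply without intervention". A low volume soon after delivery may therefore mean something different from the same low volume several days later. If so, variation in timing sits in the error term of the proof-of-concept test, and a chance difference in timing between the arms is not adjusted for in the primary estimate. What is at stake is precision in a trial of 100 women that has about 80% power in the least favourable case tabulated for its design effect.

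**Working it through.** **Inputs from the documents.** Windows of 96-144 h and 96-192 (+4) h (section 3.6.1). 100 women, 50 per arm; 50% increase; 30% drop-out; power 80.2% at within-subject correlation 0.8 and 92.3% at 0.6 (section 9.1, Table 7). Two-sided 5% test (section 9.6.1).

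**The plan's own figure.** The 80.2% cannot be reproduced independently, because the means and variances used in the simulation are not given. When simple models are calibrated to that cell, most other cells of Table 7 are not matched (for a 30% increase at correlation 0.8, 39-46% against the stated 52.1%). With the inputs undisclosed, this does not show that the table is wrong. I take 80.2% as the starting point.

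**Window width.**
- Before: 144 − 96 = 48 h.
- After: 192 − 96 = 96 h, or 196 − 96 = 100 h with the allowance; 96/48 = 2.0 and 100/48 = 2.08.
- In days postpartum: 96/24 = 4 to 192/24 = 8 (196/24 = 8.2).

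**Spread of timing, assuming times uniform over the window.**
- SD = width/√12: 13.9 h before; 27.7 h (96 h) or 28.9 h (100 h) after.
- Standard error of a chance between-arm difference in mean time = SD × √(2/50): 2.8 h before, 5.5-5.8 h after.
- The variance that a given linear timing effect can explain grows by a factor k = 2.0² = 4.0 to 2.08² = 4.3. The share becomes kR²/(1 − R² + kR²): 0.01 becomes about 0.04, and 0.02 about 0.08.

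**Power with timing in the model.** Let R² be the share of residual between-subject variance that timing explains after baseline volume and gestational age group. The documents give no value, so a range is assumed.

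Power = Φ[(z₀.₈₀₂ + 1.96)/√(1 − R²) − 1.96], with z₀.₈₀₂ + 1.96 = 2.809.

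| Assumed R² | From 80.2% |
|---|---|
| 0 | 80.2% |
| 0.02 | 81.0% |
| 0.05 | 82.2% |
| 0.10 | 84.2% |

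From 92.3%, the same formula gives 93.5% at R² = 0.05 and 94.6% at 0.10.

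**Validity without the covariate.** This was simulated in a simple linear model (n = 100, 20,000 runs per scenario, R² from 0 to 0.20). With timing omitted, the mean null estimate lay between −0.002 and 0.002 SD and type I error was 4.7-5.4%. With timing included, type I error was 4.8-5.3%. Only the spread of the estimate changed: 0.198 against 0.189 SD at R² = 0.10, and 0.201 against 0.182 at 0.20.

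**Cost in degrees of freedom.** At subject level, 100 less four terms (intercept, treatment, baseline, gestational age group) leaves about 96; timing takes one more.

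**The case against.** A reader might infer that the plan itself treats timing as prognostic. It does not. The stated aim of the timing analysis is effect modification, and the delayed-lactogenesis sentence explains why nobody is randomised before 96 h. It does not compare 96 h with 196 h, and a gradient continuing inside the window is an inference. On the wider window the plan says only that it comes "with a negligible risk for any negative impact on induction of lactation". That remark concerns harm to lactation and does not settle whether outcome varies with postpartum age.

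A reader might also infer that the proof-of-concept test is biased or invalid, or that chance imbalance is left entirely uncorrected. Neither holds. Under randomisation, chance imbalance is already reflected in the standard error. The sensitivity model contains the timing main effect, so its treatment effect evaluated at the mean time would be adjusted for timing. However, section 9.6.2 does not specify that evaluation, and no planned model fits the main effect without the interaction.

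The gain may also be smaller than the nominal window suggests. Sites are to randomise as early as possible. First enrolment was planned for Q4 2019, so women randomised before the April 2022 amendment fell under the 48 h window; the documents do not give the split. Baseline volume may take up part of any timing effect, and R² = 0 is compatible with everything in the documents.

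Finally, each Table 7 cell rests on 1,000 simulated trials, so 80.2% has a Monte Carlo standard error of √(0.802 × 0.198/1000) = 1.3 points. This blurs the starting level. The gain is a difference from a common start and does not carry that noise, but for R² up to 0.05 it is no larger than the uncertainty in the benchmark (about ±2.5 points).

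These points limit the size and the wording of the concern. They do not remove the case for a nearly free covariate.

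**Conclusion.** The point holds as a minor, optional improvement. The primary model omits a pre-randomisation variable whose permitted range the amendment doubled and which the plan's rationale makes plausibly related to later volume. The likely gain is about 0 to 4 power points for R² between 0 and 0.10, starting from 80.2%, and less from the higher-powered cells of Table 7. This rests on an assumed R², a linear timing effect and a large-sample approximation; the spread figures also assume uniform times over the window. The omission does not threaten the validity of the proof-of-concept conclusion.

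**What to change.** Add hours from delivery to randomisation as a continuous main effect in the primary repeated measures ANCOVA. Make the same edit in the synopsis, section 9.6.2 and the SAP. Keep the model with the timing-by-treatment interaction as the planned sensitivity analysis. Settle this while the team is still blinded, preferably before the futility look in section 9.9, so that the interim and final analyses use the same model.

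The cost is about one degree of freedom if timing proves uninformative. Because the primary model is written out in the protocol, the change needs a protocol amendment as well as SAP wording. No new data are needed: time of delivery is already recorded at screening, and the sensitivity model already requires the derived variable.
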